6.2. Recruitment

Xantura will identify at-risk households using data supplied by participating LAs. They will apply the predictive model shortly before the start of the first, second, and third months of the trial to ensure that risk scores are up-to-date for each batch.

For each batch, Xantura will select a target number of eligible households from each participating LA, favouring those with the highest risk scores. Households will only be eligible for inclusion in one batch, so they cannot be selected if they were part of a previous batch. Xantura will aim to select 168 households from each LA for the first batch, and then 166 for each of the second two batches (totalling 500 across all batches, though see **9.2 Attrition Assumptions** for alternative scenarios). The target of 500 households per LA was set by CHI during its project conception.

[figure not shown]
Because the sample size for each batch is capped, it is likely that some households will meet the eligibility criteria but will not be selected for that batch. When the next batch is drawn, Xantura will re-run the predictive model and any such households who still meet the eligibility criteria will be eligible for selection follow the process set out above.

6.3. Enrolment

Enrolment is automatic for selected households. We have determined that collecting informed consent for the impact evaluation would pose too great a risk to the validity of the evaluation. However, households will have the opportunity to opt out of the intervention and to opt out of their data being used in the evaluation - for more information see sections 15.2 and 16.3. Individuals in the treatment group will receive a pre-notification text message before the LA call informing them of the upcoming call and providing a link to the project's [Privacy Notice](#).

We will collect consent from any interviewees we speak to in the context of this project. Potential interview participants will be provided an information sheet and the Privacy Notice prior to them being asked if they consent to being interviewed.

6.4. Trial Flow Diagram

7. OUTCOME MEASURES

7.1. Primary Outcome

Definition

The primary outcome is a household-level binary variable indicating whether any household member is owed a relief duty as a result of a homelessness application made by or for any household member between the trial's start and the 9-month follow-up. There are two ways in which a homelessness application can result in a relief duty:

1. The application resulted in a '[relief duty](#)' being issued for that household.
2. The application resulted in a '[prevention duty](#)' which ended before the 9-month follow-up because the household or any household member became homeless.

Issuing a relief duty means the housing authority deems a household to already be homeless and accepts the duty to take reasonable steps to help the applicant secure accommodation. Issuing a prevention duty means the housing authority deems a household at risk of homelessness and accepts the duty to take reasonable steps to help prevent that. Those found to be homeless at the end of a prevention duty are consequently owed a relief duty.

Why is it measured

To determine whether the intervention achieves its ultimate aim of reducing homelessness among the target population.

Data source

Aggregated from Homelessness Case Level Information Classification ('H-CLIC') records, via the OneView platform.

When is it measured

At the 9-month follow-up.

For whom is it measured

All households enrolled in the trial.

7.2. Secondary Outcomes

The trial's secondary outcomes are focused on evidence of more proximate impact of treatment on support delivered by LAs to at-risk households. Our three (binary) secondary outcome measures of support are listed below. We will consider each at

the end of the trial (i.e., the 9-month follow-up) but also at an earlier 2-month follow-up to produce evidence of early impact on an interim basis.

Secondary outcome 1: 'Prevention Duty'

Definition

Whether a [prevention duty](#) was issued to the household or any household members (1) or not (0).

Why is it measured

To indicate whether the intervention leads to increased preventative action taken by LAs, either as a result of the call making households' need for support apparent to LAs or by resulting in earlier access to support.

Data source

Aggregated from Homelessness Case Level Information Classification ('H-CLIC') records, via the OneView platform.

When is it measured

At the 9- and 2-month follow-ups.

For whom is it measured

All households enrolled in the trial.

Secondary outcome 2: 'Council tax reduction agreement' (assuming that Xantura will be able to make this data available to us)

Definition

Whether a Council Tax reduction has been agreed for the household (1) or not (0).

Why is it measured

To indicate whether the intervention leads to improved debt management support to keep at-risk households in their current accommodation.

Data source

SHBE (Single Housing Benefit Extract) data held by LAs, via the OneView platform.

When is it measured

At the 9- and 2-month follow-ups.

For whom is it measured

All households enrolled in the trial.

Secondary outcome 3: 'Discretionary Housing Payment'

Definition

Whether a Discretionary Housing Payment was issued to any household members (1) or not (0). A discretionary housing payment is a payment designed to cover housing costs for a rent shortfall, rent deposits, or to pay rent in advance if the individual needs to move home. To be eligible, individuals must receive either Housing Benefit or the housing element of Universal Credit.

Why is it measured

To indicate whether the intervention leads to improved financial support to keep at-risk households in their current accommodation.

Data source

Revenues and Benefits records held by LAs, via the OneView platform.

When is it measured

At the 9- and 2-month follow-ups.

For whom is it measured

All households enrolled in the trial.

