5. IMPACT EVALUATION (IE)

5.1. Aims, Objectives and Hypotheses

Aims and Objectives

The IE aims to estimate the impact of LAs delivering proactive support to households deemed at risk of homelessness in the next 3-6 months on whether they are owed a relief duty.

The **primary objective** of the IE is to estimate the impact of treatment on whether households are owed a relief duty at a 9-month follow-up.

The **secondary objective** is to estimate the impact of treatment on support provided for at-risk households before the 9-month follow-up.

Research hypotheses

The **primary research hypothesis** is that allocation to treatment will reduce the likelihood of a household making a homelessness application that results in them being owed a relief duty at any point between the trial's start and the 9-month follow-up, compared to a business-as-usual (BAU) control. See 'Primary Outcome', below for the operational definition used in this trial.

The **secondary research hypotheses** are that allocation to treatment will increase the likelihood of anyone in the household being issued the following support before the 9-month follow-up:

1. A prevention duty ('Primary Outcome', below)
2. An agreed reduction in Council Tax
3. A discretionary housing payment

The trial will also consider impact on these three secondary outcomes at an earlier 2-month follow-up.

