One of the participating LAs, Test Valley, was unable to supply housing association rent arrears data, which was a key predictor in the predictive risk model. This became apparent after the originally registered version of this protocol was signed off but before any batches had been drawn for Test Valley. Therefore, Xantura developed a simplified set of criteria for identifying and sampling eligible households:

Firstly, Xantura applied a series of **inclusion criteria** for a household in Test Valley to be considered:

- Total debt (across Council Tax and Housing Benefit Overpayment (HBOP)) \geq £1000.
- Total debt \leq £8000, as households exceeding this debt threshold are commonly already known to the authorities or are refusing to collaborate.

- Current debt trend is 'Debt Increase', indicating an accelerating increase in debts over a sustained period.
- Xantura's Risk Framework metric of financial resilience is rated as 'low' or 'medium', meaning the household has low historic evidence or means of recovering from debts.
- No Discretionary Housing Payments in past 6 months.
- No homelessness duty in past 6 months.

Then, Xantura **sorted eligible Test Valley households into tiers** intended to reflect risk of homelessness. The 'highest risk' households (Tier 1) are those with rising debts for both Council Tax and HBOP, and either total debt exceeding £3,000 or evidence of homelessness in the past 18 months. The 'high risk' (Tier 2) households are those with evidence of historic homelessness alongside either rising Council Tax debt or rising HBOP debt (but not both). Lastly, 'moderate risk' households had either rising Council Tax debt or rising HBOP debt (again, not both), but with no evidence of prior homelessness.

Xantura **sampled households** for each cohort beginning with those in Tier 1. If there were not enough households in Tier 1 to meet the target sample size then they selected from Tier 2, and then from Tier 3 if necessary.

In light of these changes, we agreed the following amendments to the evaluation with CHI and Xantura:

1. Xantura will identify eligible households in Test Valley according to a simplified set of criteria rather than the predicted risk scores used in the other LAs.
2. We will randomise households in Test Valley without blocking by risk scores, which would not be available for those households. Those randomised into the intervention will receive support as specified in Section 3.

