8. DATA COLLECTION

8.1. Data collection methods

All study outcomes and planned covariates come from administrative records, which will be provided by LAs on a monthly basis and collated within the OneView platform. Additionally, call handlers will use OneView to record their attempts and success at making the treatment calls to support the compliance analysis and IPE. Xantura will have responsibility for managing data collection, ensuring data quality, and minimising missing information. They will provide household-level risk scores for the randomisation and then will deliver outcome data at the 2-month and 9-month follow-ups.

Timelines

For each batch, the trial will begin with randomisation, followed by a 1-month intervention period in which LAs deliver the calls to treatment households, with the two follow-up data collection points occurring 2 and 9 months after the end of the intervention period.

Table 6: Data collection procedures and assessment timeline

Assessment point	Type of data	Data collection approach
Pre-trial Batch 1: April 2025 Batch 2: May 2025 Batch 3: June 2025	Baseline characteristics of the sample All administrative data from LAs Risk scores from Xantura's predictive model (for randomisation)	Data collected from LA records by Xantura via OneView
1-month Intervention period Batch 1: May 2025 Batch 2: June 2025 Batch 3: July 2025	Outcomes related to the proactive call made to individuals in at risk households.	Data collected from LA call handlers by Xantura via OneView
2-month follow-up Batch 1: July 2025 Batch 2: August 2025 Batch 3: September 2025	Secondary outcome data	Data collected from LA records by Xantura via OneView

9-month follow-up Batch 1: February 2026 Batch 2: March 2026 Batch 3: April 2026	Primary outcome data Secondary outcome data	Data collected from LA records by Xantura via OneView
---	--	---

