10.4. Secondary analyses

Our secondary analyses will follow the same approach as the primary analysis but replacing the outcome measure with the three specified secondary outcome measures:

- Whether a prevention duty was issued to any household members (1) or not (0)
- Whether a Council Tax reduction was issued to any of household members (1) or not (0)
- Whether a Discretionary Housing Payment was issued to any household members (1) or not (0)

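### The Council Tax reduction outcome, and less clearly the Discretionary Housing Payment outcome, have no start date or baseline adjustment, so awards made before randomisation can count and dilute the effect

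*Protocol*

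**What the plan says.** Section 7.2 defines secondary outcome 2 as "Whether a Council Tax reduction has been agreed for the household (1) or not (0" and secondary outcome 3 as "Whether a Discretionary Housing Payment was issued to any household members (1) or not (0". Both are measured at the 2-month and 9-month follow-ups. That fixes when the data are pulled, not the period in which an award counts.

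The secondary hypotheses in section 5.1 supply an upper bound only: "allocation to treatment will increase the likelihood of anyone in the household being issued the following support before the 9-month follow-up". The primary outcome in section 7.1 has both ends, because it covers applications made "between the trial's start and the 9-month follow-up".

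On the model, section 10.4 states: "Our secondary analyses will follow the same approach as the primary analysis but replacing the outcome measure". The primary model in section 10.3 contains treatment, risk score and LA, so receipt of the same support at baseline is not a term.

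On eligibility, section 6.1 excludes households with a relief or prevention duty in the last 6 months, but not those with an existing Council Tax reduction or DHP. The only such screen, "No Discretionary Housing Payments in past 6 months", applies to Test Valley (section 5.2), and the same section removes Test Valley from the secondary analyses.

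Table 6 in section 8.1 lists "All administrative data from LAs" among the data collected before each batch.

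**The concern.** A Council Tax reduction can be a standing arrangement. If it was agreed before randomisation, the call cannot change the household's score, yet under the section 7.2 wording the household scores 1. The trial selects households using debt and benefit data, so some existing awards are plausible.

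Section 7.2 presents the secondary outcomes as the more proximate evidence that the intervention leads to support. Section 3.2 accepts that a null primary result could reflect either no rise in engagement or ineffective services. If the support outcomes carry households whose score is already settled, they are less able to help interpret such a null. The 2-month versions are the more exposed, because fewer new awards can accrue in the shorter window.

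The descriptive list in section 10.2 asks when prevention and relief duties were issued, but does not ask for timing of Council Tax reductions or DHPs. The planned tables would therefore not reveal the problem.

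**Working it through.** **The plan's own figure.** Scenario C (sections 9.2 and 9.3) gives 4 LAs × 500 × 0.8 = 1,600 households, 800 per arm, with a minimum detectable effect of 2–7 percentage points. A two-proportion normal calculation (two-sided 5%, 80% power) gives 6.98 points at a 50% base rate and 1.5–2.0 points at base rates of 2–3%, so the stated range reproduces. It is for the primary outcome. The protocol states no power for outcomes 2 and 3.

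**Inputs for the secondary outcomes.**
- Households: Test Valley is out, so 3 × 500 × 0.8 = 1,200, or 600 per arm.
- New-award rates among households without a prior award: 10% control and 15% treatment. This is an assumption.
- Share b already holding an award, equal in both arms by randomisation: unknown, shown from 5% to 50%.
- Covariates explain nothing, as section 9.1 assumes for the primary outcome. Prior holders are taken to receive no further new award.

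**Formulas.** With new-award rate p in an arm:
- As worded: rate = b + (1 − b)p.
- New awards only, all households kept: rate = (1 − b)p.
- Power = Φ[(d − 1.96 × SE0) / SE1], where d is the arm difference, SE0 the pooled standard error and SE1 the unpooled one.

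In both cases d = (1 − b)(0.15 − 0.10). On the percentage-point scale the wording therefore adds noise and leaves the difference unchanged. On the odds-ratio scale, which the planned logit model estimates, it also pulls the effect towards 1.

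**Worked case, b = 10%.**
- As worded: 19.0% against 23.5%, d = 0.045, SE0 = 0.02362, SE1 = 0.02358. Power = Φ[(0.045 − 0.0463)/0.02358] = 48%. Odds ratio = (0.235/0.765)/(0.190/0.810) = 1.31.
- New awards only: 9.0% against 13.5%, d = 0.045, SE0 = 0.01824, SE1 = 0.01820. Power = Φ[(0.045 − 0.0358)/0.0182] = 69%. Odds ratio = (0.135/0.865)/(0.090/0.910) = 1.58.

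| Prior holders b | d (points) | Odds ratio, as worded | Odds ratio, new only | Power, as worded | Power, new only |
|---|---|---|---|---|---|
| 0% | 5.00 | 1.59 | 1.59 | 75% | 75% |
| 5% | 4.75 | 1.41 | 1.58 | 59% | 72% |
| 10% | 4.50 | 1.31 | 1.58 | 48% | 69% |
| 30% | 3.50 | 1.16 | 1.56 | 24% | 57% |
| 50% | 2.50 | 1.11 | 1.54 | 14% | 43% |

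Using the unpooled standard error throughout raises these powers by less than one percentage point.

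**What the baseline term adds once the outcome is dated.** Restricting to non-holders gives a rough guide: power is 70%, 59% and 46% at b = 10%, 30% and 50%, against 69%, 57% and 43% above. The date window does most of the work.

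**The case against.** The best counter-argument is that new awards are plainly intended. The hypotheses are about what allocation changes, and allocation cannot change earlier awards. Section 10.4 words the Council Tax outcome as something issued, and the DHP is always worded that way. A derivation window is also a detail that a statistical analysis plan, not shown here, might settle. This stands as far as intent goes: a reader should not infer that the protocol deliberately counts prior awards. It does not remove the point, because the definition in section 7.2 describes a status, the primary outcome shows that the authors state a start where they mean one, and the model is already fixed without baseline receipt.

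Other objections stand in part.
- Section 10.3 defends a parsimonious model, and randomisation balances prior receipt in expectation. Leaving out the covariate is therefore a loss of precision, not an error that favours an arm.
- Availability of the data is not assured. Section 7.2 makes outcome 2 conditional on the data provider supplying it, and section 10.8 says that baseline measures needed for imputation will not be present.
- The outcomes differ. The case is clear for Council Tax reduction and weaker for DHP. The prevention duty is also undated, but is partly protected by the 6-month exclusion.

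A reader might go further and infer that prior awards swamp any effect, or that a real effect will probably be reported as null. The protocol gives no prevalence, so neither follows. At 2% prior holders the loss is only from 74% to 68%. Even with new awards only, power stays below 80% under the assumed effect.

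**Conclusion.** The point holds as a defect of definition, with consequences for precision. As written, secondary outcome 2 and, less clearly, secondary outcome 3 allow awards made before randomisation to score 1 in the three analysed LAs, and the secondary models do nothing to offset this. The result is an odds ratio pulled towards 1 and lower power, with no systematic advantage to either arm.

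The size cannot be fixed from the protocol. Under the assumptions above, the wording costs about 13 percentage points of power at 5% prior holders, 22 at 10%, 34 at 30% and 29 at 50% (differences taken before rounding). These figures illustrate the Council Tax outcome. They should not be carried over to DHP without a separate view of how common earlier payments are. The primary outcome is unaffected.

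**What to change.** - Define secondary outcomes 2 and 3 as an award with a decision date from the household's randomisation up to the follow-up in question, counted over all randomised households. Align the prevention-duty wording in the same way.
- Where the pre-trial or monthly LA extract holds it, add receipt of the same support at randomisation as a covariate in the corresponding model. Check for separation: if all prior holders share one outcome value, the logit coefficient for that term is not finite.
- If no decision date can be supplied, derive a new award as receipt at follow-up without receipt in the baseline extract, or at least adjust for baseline receipt.
- Report the share of prior holders by arm and LA, so that the extent of the problem is visible.

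The cost is one line per outcome and a date field or baseline flag requested from the data provider. Whether these fields reach the evaluator should be confirmed first, given the caveats in sections 7.2 and 10.8. The change applies equally to both arms and can be made through the addendum route in section 13.2 before analysis. If 2-month results have already been produced under the present wording, the report should say so.

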8. DATA COLLECTION

8.1. Data collection methods

All study outcomes and planned covariates come from administrative records, which will be provided by LAs on a monthly basis and collated within the OneView platform. Additionally, call handlers will use OneView to record their attempts and success at making the treatment calls to support the compliance analysis and IPE. Xantura will have responsibility for managing data collection, ensuring data quality, and minimising missing information. They will provide household-level risk scores for the randomisation and then will deliver outcome data at the 2-month and 9-month follow-ups.

Timelines

For each batch, the trial will begin with randomisation, followed by a 1-month intervention period in which LAs deliver the calls to treatment households, with the two follow-up data collection points occurring 2 and 9 months after the end of the intervention period.

Table 6: Data collection procedures and assessment timeline

Assessment point	Type of data	Data collection approach
Pre-trial Batch 1: April 2025 Batch 2: May 2025 Batch 3: June 2025	Baseline characteristics of the sample All administrative data from LAs Risk scores from Xantura's predictive model (for randomisation)	Data collected from LA records by Xantura via OneView
1-month Intervention period Batch 1: May 2025 Batch 2: June 2025 Batch 3: July 2025	Outcomes related to the proactive call made to individuals in at risk households.	Data collected from LA call handlers by Xantura via OneView
2-month follow-up Batch 1: July 2025 Batch 2: August 2025 Batch 3: September 2025	Secondary outcome data	Data collected from LA records by Xantura via OneView

9-month follow-up Batch 1: February 2026 Batch 2: March 2026 Batch 3: April 2026	Primary outcome data Secondary outcome data	Data collected from LA records by Xantura via OneView
---	--	---

8.2. Retention strategies

Given that the recruitment and assessment processes are driven by administrative data, and that the intervention does not require ongoing compliance on behalf of the household contacted by the LA, retention is not expected to be a significant challenge in this evaluation.

In order to promote engagement with the intervention, a lead adult of each household in the intervention arm will receive a pre-notification text message alerting them to the fact that they will receive a phone call from their LA. Households in the control arm will not be notified that they are included in the trial.

There are no additional incentives offered to participants for participation in this trial.

9. SAMPLE SIZE AND POWER CALCULATION

9.1. Sample Size / Power Calculation

There is little evidence at present for the likely scale of any treatment effects, or for the distribution of baseline risk scores in each participating LA or how well they really predict future homelessness. Each of these could impact power. Furthermore, the sample size is limited by the number of at-risk households in the population and LAs' capacity to deliver the treatment, of which we expect the latter to be more limiting. We therefore start here from the planned sample size that LAs initially consented to when they agreed to take part (500 per LA) and consider the implications of various scenarios in which the achieved sample is lower than planned due to delivery constraints or attrition (e.g., missing data), under a set of conservative assumptions.

We present below the Minimum Detectable Effect Size (MDES) for effect of treatment on the (binary) primary outcome measure under each scenario. MDES are shown as absolute percentage point differences, provided as ranges because they vary depending on baseline proportions. To minimise the risk that our power calculations overstate power, we make the conservative assumption that the planned baseline covariates do not account for any variance in the primary outcome. This is in practice unlikely to be the case, although they may not greatly improve power if baseline risk scores are high in most sampled households.

Under our assumed likely scenario, our MDES at alpha = 0.05 and power (beta) = 0.8 is a 2-7 absolute percentage point difference in the proportion of households becoming homeless between treatment and control. Ranges are provided because the MDES expressed in absolute terms varies with base probability of homelessness under the null hypothesis (Figure 3).

